Endpoint	The primary outcome will be the percentage of swallows with aspiration and/or penetration for cold milk compared with room temp milk (a total of 15 swallows will be assessed by VFSS and FEES). Based on our preliminary results, we expect to find a significant decrease in penetration and aspiration during the initial cold swallows (5 swallows). We expect this improvement to be sustained on the subsequent cold swallows (10 swallows) following the 15-minute cold liquid feeding. A decrease of 30% in penetration and/or aspiration with cold milk will be considered significant. Similarly, a 30% improvement of feeding coordination as assessed by nFant device will be considered significant.
	2. Evaluate the safety of feeding cold milk in preterm infants. We will evaluate whether cold milk will cause hypothermia (assessed by measuring Axillary temperatures), change in vital signs (respiratory rate, heart rate, and oxygen saturation) as well as change in mesenteric blood flow indices (assessed by abdominal ultrasound) These changes with cold milk feeding will be expressed as % change compared to base line (room temp milk).
Study Duration	2 years
Participant Duration	The subjects will participate in the study for approximately 48 hours during their NICU hospital stay
Population	Preterm Infants less than 34 weeks gestation admitted to NYU- Langone Long Island Hospital NICU. (n=42)
Study Sites	NYU- Langone Long Island Hospital
Number of participants	42

1. Introduction, Background Information and Scientific Rationale

Approximately half a million preterm infants are born every year in the USA.^{1,2} It is estimated that 30-70% of very low birth weight (VLBW) preterm infants will be diagnosed with swallowing dysfunction (dysphagia), with an inverse relationship between the severity of dysphagia and gestational age (GA).³⁻⁶ Although the pathophysiology of dysphagia is multifactorial,^{4,7-9} the discoordination between swallowing and breathing is the most prevalent cause of dysphagia in preterm infants,¹⁰ which often leads to airway compromise in the form of laryngeal penetration and/or tracheal aspiration into the lungs.^{7,11} Chronic airway compromise results in a persistent inflammatory state, with disease progression to chronic lung injury and *bronchopulmonary dysplasia (BPD)* that can be devastating for already fragile and developmentally immature lungs in preterm infants.^{4,7}

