- The axillary temperature will be measured immediately prior to and after each feeding condition. It will also be measured at 10, and 30 minutes after the CS feed, at the same time the gastric content temperatures are taken. Infants' vital signs will be recorded (blood pressure, respiratory rate, heart rate, and oxygen saturation), as well as evidence of bronchospasm, lethargy, respiratory distress, apnea, tachypnea, cyanosis, bradycardia, or tachycardia.
- Doppler ultrasound (Sonosite Edge Ultrasound system, Sonosite, Inc, WA) will be used to measure
 intestinal blood flow indices including the superior mesenteric artery flow (SMA), peak systolic velocity,
 SMA mean velocity, SMA end-diastolic velocity, resistive index, pulsatility index, portal vein volumetric
 blood flow, as well as heart rate and mean arterial blood pressure. Intestinal blood flow monitoring via
 Doppler ultrasound will be performed 6 times for each participant, performed one hour before and at 30 and
 60 minutes after both bedside feeding conditions (RTS and CS). Measurements will be taken at the bedside
 in the supine position.
- Step 2 (done 24-48 hours after step 1):
 - Infants will be transported to the radiology suite and undergo VFSS and or FEES, as ordered by the treating
 medical team (Figure1: the blue boxes indicate procedures done for research purpose only. None of the
 research procedures are experimental and are approved tests for neonates including VFSS, FEES, nfant
 test and abdominal ultrasound).
 - Routine procedure for VFSS or FEES will be followed as ordered by the medical team. This procedure is part of the routine clinical care and not considered part of the research study.
 - If no dysfunction is noted, the procedure will end, and the child will no longer be eligible for further participation in this research study. If dysfunction (penetration/aspiration) either on the VFSS or FEES study is noted, the child will be eligible to participate in the next phase of the study.
 - Immediately following the initial VFSS-FEES assessment, the infants will remain in the same seated position with the FEES scope in place. While keeping all variables from the standard VFSS-FEES the same, the infant will be fed cold barium (4-9°C) using the same nipple. A total of 5 swallows will be visualized using VFSS and FEES, labeled "Cold Swallows-1 (CS1)." These 5 swallows assessment are done for the research purpose only.

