Axillary temperatures, as well as mesenteric blood flow indices, will be compared between the CS and RTS feeds. A Two One-Sided Test (TOST) will be used to evaluate whether the body temperature and blood flow indices are equivalent before and after the cold liquid swallow. Equivalence will be determined if the 90% confidence interval of pre-post change is contained within the predefined margin of ± 0.5 . *Power and sample size:* The study subjects are the same subjects enrolled in Aim 1 (n=42). We have simulated data assuming a margin of equivalence from - 0.5° C to 0.5° C, significance level 0.05, TOST and 10000 Monte Carlo samples. With the planned sample size for aim 1 (N=42), we will have sufficient power (>80%) to detect equivalence when the margin of equivalence is from - 0.5° C to 0.5° C and the actual mean difference is zero.

5. Study Enrollment

Inclusion Criteria

 Viable preterm infants less than 34 weeks gestation), 2) admitted to NYU- Langone Long Island Hospital NICU, 3) PMA > 35 weeks at the time of the study, 4) receiving no or minimum respiratory support (<2 lit/min low-flow nasal cannula), 5) tolerating at least 50% of their enteral feeding orally and 6) having symptoms of swallowing dysfunction during oral feeding (clinical dysphagia). 7) referred by the medical team for VFSS and/or FEES assessments.

Exclusion Criteria

Exclusion criteria include children with other comorbidities, such as IUGR, upper airway anomalies, brain injury, neuromuscular disease, or life-threatening congenital disease.

Total Number of Participants and Sites

We will need 42 subjects over a 2 years period.

Vulnerable Subjects

Our population will include children by nature of the study objectives.

The study has potentially greater than minimal risk, but there is possible direct benefit to the individual subject. Although previous studies as well as our preliminary study didn't show any evidence of cold stress in response to cold milk feeding, it is a potential risk. In addition there will be minor increase in radiation exposure as described previously. Currently there is no effective treatment for dysphagia in preterm infants. The results of this research (the safety and effectiveness of cold milk for each subject) will be disclosed to the medical team. If the results confirm safety and efficacy for that infant, the medical team can consider using cold milk to treat the infant's dysphagia which can be a significant benefit to the subject.

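### The Aim 2 equivalence rule applies a ±0.5 margin, given a unit only as °C, to every mesenteric Doppler index, so blood-flow equivalence has no usable margin, SD or power

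*Combined protocol and SAP*

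**What the plan says.** **Decision rule.** Section 4, Statistical Considerations, aim 2 uses a TOST to judge "whether the body temperature and blood flow indices are equivalent before and after the cold liquid swallow". One criterion serves both kinds of endpoint: "Equivalence will be determined if the 90% confidence interval of pre-post change is contained within the predefined margin of ± 0.5". No unit follows the number in the text as supplied.

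**Power.** The same paragraph claims more than 80% power with N=42 "when the margin of equivalence is from - 0.5° C to 0.5° C and the actual mean difference is zero". It states no SD and does not mention blood flow.

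**Doppler indices.** Section 4, Step 1 lists superior mesenteric artery flow, three velocities (peak systolic, mean, end-diastolic), the resistive and pulsatility indices, and portal vein volumetric flow. Six scans are planned: one hour before, and 30 and 60 minutes after, each of the two bedside feeds.

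**Scale and contrast.** The synopsis (Endpoint, item 2) says of the safety measures, temperature and vital signs included: "These changes with cold milk feeding will be expressed as % change compared to base line (room temp milk". The analysis section first says "Axillary temperatures, as well as mesenteric blood flow indices, will be compared between the CS and RTS feeds" and then describes a before-and-after test around the cold feed.

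**Temperature schedule.** Step 1 takes axillary readings just before and just after both feeds. For later readings it says only: "It will also be measured at 10, and 30 minutes after the CS feed". Step 2 adds axillary readings every 10 minutes.

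**Role.** The synopsis and section 3 state as a hypothesis that cold milk does not harm intestinal blood flow on Doppler. Section 3 makes confirming safety the second objective.

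**The concern.** An equivalence margin has meaning only in the unit of the variable it bounds. Half a degree is intelligible for axillary temperature. The same 0.5 cannot serve as a common bound for a velocity, a dimensionless ratio and a volumetric flow. The plan ties it neither to a unit for the indices nor to the percentage scale in the synopsis.

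This TOST is the only blood-flow analysis with a decision rule, so it is what would support or refute the blood-flow hypothesis. If the unit, contrast and time point are settled after data are seen, those choices could decide the answer. Section 4 also says that, if efficacy and safety are shown, clinicians could use cold milk without repeating the study's safety measurements in each child. A group-level equivalence claim may therefore carry weight after the trial.

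**Working it through.** **Inputs from the plan:** margin Δ = 0.5; n = 42; significance level 0.05 per one-sided test (matching the 90% CI); true mean change zero. **Not in the plan:** the SD of paired change, for temperature or any index. Every SD below is an assumption.

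**Rule.** With mean paired change d and observed SD s, equivalence is declared when |d| + t × s/√n < Δ. Here t(0.95, 41 df) = 1.683 and √42 = 6.481.

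**1. The plan's own figure (temperature, ±0.5 °C).** It cannot be reproduced without an SD, so solve for the SD that it needs.
- Normal approximation: SD = Δ√n/(z0.95 + z0.90) = 0.5 × 6.481/(1.645 + 1.282) = 1.11 °C.
- Exact calculation, integrating over the distribution of s: 1.09 °C.
- Exact power: 99.1% at SD 0.75, 87.7% at 1.0, 78.9% at 1.1, 36.9% at 1.5.

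The claim of more than 80% therefore holds if the SD of paired temperature change is about 1.09 °C or less, with all 42 pairs complete. With 36 pairs and SD 1.0 °C, power is about 80%.

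**2. The rule taken literally for a velocity.** No pair of limits can lie inside ±0.5 once s exceeds 0.5 × 6.481/1.683 = 1.93, in whatever unit is recorded.
- Assumed SD 10 cm/s: half-width 1.683 × 10/6.481 = 2.60, more than five times the margin. Power 0%.
- The same data in m/s, SD 0.10: half-width 1.683 × 0.10/6.481 = 0.026. Power 100%.

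The infants and measurements are the same, and only the unit has changed.

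**3. The rule taken literally for the resistive index.** Suppose a true fall of 0.3.
- SD 0.2: half-width 1.683 × 0.2/6.481 = 0.052, so the expected interval is −0.352 to −0.248, well inside ±0.5. To fail, the observed mean would have to be below about −0.448, which is (0.448 − 0.300)/(0.2/6.481) = 4.8 standard errors away.
- SD 0.1, 0.15 and 0.2: equivalence is declared in about 100% of trials.

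**4. Other readings, none of them stated in the plan (n = 42).**

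| Reading of ±0.5 | Result |
|---|---|
| 0.5 percentage points, no true change | power 4% at SD 2 points, 0% at SD 5 or more |
| 50%, true mean fall of 30% | declared equivalent in 99.5% of trials at SD 30 points, 82% at SD 50 |
| 0.5 SD of the paired change, no true change | power 87.7% |

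**5. General relation.** For 80% power with 42 pairs and no true change, the margin must be about 0.5/1.089 = 0.46 times the SD of paired change, in the index's own unit. Without an SD and a margin for an index, its power cannot be stated.

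**6. Contrast and time point.** The synopsis takes room-temperature milk as the baseline. The analysis section names both a between-feed comparison and a pre-post test around the cold feed. It does not say whether the 30- or the 60-minute scan is tested. For temperature, the 10- and 30-minute readings in Step 1 follow the cold feed only, so a between-feed post-feed contrast is available there only immediately after feeding.

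**The case against.** **The unit may have been lost in text extraction.** There is a stray space after the 0.5 in the rule, and the next sentences give the margin in °C. This is plausible, and the missing unit should not be counted as an error in itself. But if the rule reads ±0.5 °C, the blood-flow indices it names have no margin at all. The defect survives either way.

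**A standardised margin may have been meant.** Half an SD would apply to every index and give 87.7% power. The plan does not say so, and its power statement is in °C. The reading does show that ±0.5 need not be either unattainable or far too lax. The figures in steps 2 to 4 illustrate what the wording allows, on assumed SDs; they do not predict this trial's result.

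**The percentage scale may only be a reporting convention.** That is possible. It covers temperature too, so a °C test leaves temperature off that scale as well. The two sections need reconciling rather than one overriding the other.

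**The temperature contrast is fairly clear.** Readings just before and just after the cold feed are the natural pair. This largely stands, although the later readings leave the tested time unnamed.

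**A reader might infer that the temperature test is underpowered.** The documents do not support that. They omit the SD, and the claim holds for any SD up to about 1.09 °C with complete pairs.

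**A reader might also infer that infants are less well protected.** The documents do not support that either. Adverse-event criteria, stopping rules and DSMB review do not use the TOST, and results passed to treating teams concern the individual infant.

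**Conclusion.** The point holds and must be fixed. One TOST rule covers temperature and all Doppler indices with a margin that has a unit only for temperature. No Doppler index has a usable margin, SD or power, so the stated blood-flow hypothesis has no interpretable equivalence test.

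Taken literally, the rule gives 0% or 100% power for the same velocity data according to unit (assumed SD 10 cm/s, 42 pairs, no true change). It also passes a resistive-index fall of 0.3 in about 100% of trials (assumed SD 0.1 to 0.2). These figures rest on assumed SDs and on the raw-unit reading; the absence of a Doppler margin rests on the text alone. The synopsis and analysis section also disagree on scale and contrast, and no post-feed test time is named.

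The conclusion goes no further. The temperature power claim is unverified, not refuted, and the primary outcome is unaffected.

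**What to change.** - **Temperature.** Limit ±0.5 to axillary temperature in °C. State the SD behind the power of more than 80%, and say that this power covers temperature only.
- **Blood flow.** For each Doppler index on which equivalence will be claimed, set a margin in its own unit or as a relative change, justified by the sponsor. Report the remaining indices descriptively with 90% CIs and make no equivalence claim for them.
- **Scale, contrast, time.** Reconcile the synopsis and the analysis section on both scale and contrast, and name the post-feed time point or points tested. One option that the six planned scans allow, though not a requirement, is log(post/pre) for the cold feed minus log(post/pre) for the room-temperature feed.
- **Timing.** Fix these choices before any interim results are reviewed. Under DSMB Responsibilities, an interim analysis is presented after every 10 infants, so waiting until final analysis is too late.

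**Cost.** SAP wording and the sponsor's work in justifying margins; no new data or procedures. The downside is that the plan must state openly that blood-flow equivalence currently has no stated power.

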Our preliminary data (REF) showed a mean change of 44 and 36% in aspiration and penetration, respectively. For power computation, we conservatively assumed an average change of 30% and a common standard deviation of 25 in both aspiration and penetration. We simulated data using a two-sided Wilcoxon Signed-Rank Test (the non-parametric equivalent of the paired t-test) with alpha=0.05 significance level and a pre-post correlation of 0.20, which revealed that a sample size of N=25 subjects would provide us more than 95% power to detect a large effect size both in aspiration and penetration. These simulation results are based on 10000 Monte Carlo samples. Assuming a conservative estimate that 60% of infants with clinical dysphagia will have a positive VFSS or FEES test, we expect that we will need to enroll 42 subjects to have 30 subjects with a positive dysphagia test.

Informed Consent Process

Informed consent is a process that is initiated prior to the individual's agreeing to participate in the study and continues throughout the individual's study participation. Extensive discussion of risks and possible benefits of participation will be provided to the infants' parents. Consent forms will be IRB-approved and the parents (defined as either the mom or dad if they are legally married) will be asked to read and review the document. The study investigators will explain the research study to the parents and answer any questions that may arise. All participants will receive a verbal explanation in terms suited to their comprehension of the purposes, procedures, and potential risks of the study and of their rights as research participants. Parents will have the opportunity to carefully review the written consent form and ask questions prior to signing. The parents should have the opportunity to discuss the study with their surrogates or think about it prior to agreeing to participate. The parents will sign the informed consent document prior to any procedures being done specifically for the study. The parents may withdraw consent at any time throughout the course of the study. A copy of the signed informed consent document will be given to the parents for their records. The rights and welfare of the participants will be protected by emphasizing to them that the quality of their medical care will not be adversely affected if they decline to participate in this study.

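### Enrolling 42 infants at a 60% positive rate yields about 25 test-positive infants, not the 30 the sample-size statement gives

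*Combined protocol and SAP*

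**What the plan says.** The sample-size text appears twice in the same words on this point: under Statistical Considerations at the end of Section 4, and in Section 6 (Sample Size Determination). It has three parts.

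- **Power.** A simulation of the two-sided Wilcoxon signed-rank test (alpha 0.05, mean change 30, SD 25, pre-post correlation 0.20) is reported to show that "a sample size of N=25 subjects would provide us more than 95% power to detect a large effect size both in aspiration and penetration".
- **Positive rate.** "Assuming a conservative estimate that 60% of infants with clinical dysphagia will have a positive VFSS or FEES test".
- **Enrolment.** From that rate, "we expect that we will need to enroll 42 subjects to have 30 subjects with a positive dysphagia test".

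Two other places fix how these figures are to be read. Section 5 makes clinical dysphagia an inclusion criterion. Section 4, Step 2, says of an infant whose routine test is normal: "If no dysfunction is noted, the procedure will end, and the child will no longer be eligible for further participation in this research study".

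**The concern.** The enrolment sentence derives 42 from a positive rate and a target number of positives, so the three numbers should satisfy enrolled × rate = positives. They do not: 60% of 42 is about 25.

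The number matters because a positive test is the entry condition for the cold-swallow assessments in Step 2, from which the primary outcome is computed. It is therefore the largest number of infants who can supply those data. A reader who sees 30 positives beside a power calculation for 25 will naturally infer five infants to spare. The plan's own assumptions leave no such reserve. The DSMB, which reviews accrual, would also be comparing it with an expected yield that is too high.

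**Working it through.** **Inputs (all from Section 6 unless noted)**

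- Enrolled: 42 (also the synopsis and Section 5)
- Positive rate among infants with clinical dysphagia: 60%
- Stated number positive: 30
- Number used for power: 25
- Denominator: every enrolled infant has clinical dysphagia (Section 5), so the 60% applies to all 42

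**Step 1. Try to reproduce the stated 30**

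Expected positives = enrolled × rate = 42 × 0.60 = 25.2. The stated 30 is not reproduced. The difference is 30 − 25.2 = 4.8 infants, 16% of the stated figure, which is too large for rounding.

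**Step 2. Work backwards**

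- Enrolment needed for an expected 30 at 60%: 30 / 0.60 = 50.
- Rate needed for an expected 30 from 42: 30 / 42 = 71.4%.

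**Step 3. Where could 42 have come from?**

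- 25 / 0.60 = 41.7, rounded up to 42. This is the correct calculation for the powered number of 25, in which case 30 is the misstatement.
- 30 × 1.40 = 42. This multiplies by one plus the 40% loss instead of dividing by 0.60, in which case 42 is the mistake.

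Both routes give 42, and the documents do not show which was used. They give no second rate or attrition allowance linking 42 to 30; attrition would in any case lower the yield.

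**Step 4. Spread of the yield**

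These figures are exact binomial and treat each rate as known.

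| Enrolled | Rate | Expected positives | 5th to 95th percentile | P(at least 25) | P(at least 30) |
|---|---|---|---|---|---|
| 42 | 60% | 25.2 | 20 to 30 | 59.1% | 8.6% |
| 50 | 60% | 30 | 24 to 36 | 94.3% | 56.1% |
| 42 | 71.4% | 30 | 25 to 35 | 96.7% | 57.7% |

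**Step 5. Does the power claim survive?**

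The SD of the paired difference is 25 × √(2 × (1 − 0.20)) = 31.6. Simulating the two-sided Wilcoxon signed-rank test with mean difference 30 (10,000 runs; normally distributed differences are an assumption of this check, not of the documents) gives:

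| Infants analysed | Power |
|---|---|
| 25 | 0.99 |
| 20 | 0.98 |
| 18 | 0.96 |
| 15 | 0.92 |

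The claim of more than 95% at 25 stands. With 42 enrolled at 60%, the chance of at least 20 positives is 96% and of at least 18 is 99%.

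**The case against.** The strongest reply is that nothing of substance turns on the error. The power statement is for 25 infants and 42 enrolled delivers about 25, so enrolment and power already agree and the 30 is a stray number. On the plan's assumptions, power stays above 95% down to about 18 positives, so the 59% chance of reaching 25 should not be read as a 41% chance of an underpowered trial. The safety power statement uses all 42 and is untouched. This is right, and it limits the point to the stated yield.

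Three further points can be made.

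- The plan calls 60% conservative, so the true yield may be higher. That is possible, but the sentence derives the enrolment from 60%, and the arithmetic has to follow from the rate it names.
- Section 1 reports that dysphagia occurrence in the group's pilot study was 71% before cold liquid, close to the 71.4% that would make 42 and 30 agree. The text does not say whether that is a proportion of infants or of swallows, and the sample-size section does not use it, so it does not reconcile the figures.
- No passage describes the gap between 30 and 25 as a reserve. That is an inference from seeing the two numbers together.

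One refinement points the other way. Step 2 also ends participation for infants whose dysphagia does not improve over the first five cold swallows. The count of positives therefore applies to that first assessment, and is only an upper bound for the later ten swallows.

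**Conclusion.** The statement is wrong as written: 42 enrolled, 60% positive and 30 positives cannot all hold. On the stated enrolment and rate the expected yield is 25.2, about five fewer than claimed, and 30 or more would occur about one time in twelve (8.6%). The point figure rests on the documents' own numbers; the probability also assumes independent infants and a true rate of exactly 60%.

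The consequence is modest. The power claim at 25 is reproduced and tolerates a shortfall, provided the assumed mean change, SD and correlation are right. The correction should be made because the plan states a yield that its own assumptions do not support, in the section that justifies the size of the trial.

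**What to change.** Correct the sentence in both places, the Statistical Considerations paragraph of Section 4 and Section 6. Keeping 42 and 60%, replace the 30 with about 25 infants expected to test positive. If a range is added, label it: 20 to 30 is the 5th to 95th binomial percentile with the rate taken as exactly 60%. The cost is two sentence edits and a less favourable yield; design, enrolment and analysis do not change.

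If the sponsor holds that 30 is the intended number, it should do one of the following:

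- justify a positive rate near 71%, saying whether the pilot figure in Section 1 is per infant; or
- state 50 enrolled at 60%. This is not a small edit, since 42 also stands in the synopsis (population and number of participants), in the Section 4 paragraph on disclosing results, in the safety power statement and in the Section 5 total.

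If the sponsor wishes to quote power at a smaller yield, such as 20, it should take the figure from its own simulation.

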 - If the dysphagia didn't improve, the study would end, and the child will no longer be eligible for participation further in this research study.
 - If the dysphagia improves with cold liquid, VFSS will then be turned off and the infants will then be fed their regular feeds (formula or expressed breast milk as indicated by the medical team) chilled to an approximate temperature of 4-9°C for a total of 15 minutes, or until the infant shows signs of feeding completion. The cold feeding will be replaced every 5 minutes to make sure that the temperature is maintained at 4-9°C to minimize habituation effect.³⁰
 - After the 15 minute period, the infant will be re-assessed by VFSS-FEES using cold barium from the same bottle (10 swallows, labeled "Cold Swallows-2" [CS2]). This design evaluates whether a full feeding of cold liquid will result in decreased penetration or aspiration compared to RTS condition. These 10 swallows assessment are done for the research purpose only).
 - The axillary temperature will be monitored every 10 minutes. Infants' vital signs (blood pressure, respiratory rate, heart rate, and oxygen saturation), as well as evidence of any respiratory compromise, will be recorded. A neonatologist will be next to the baby at all times. The baby will return to the NICU after the study accompanied by the NICU team, including the neonatologist.

Study #: i20-00876

Version Date: 6/13/2022

Depending on the scheduling of the VFSS/FEES testing by the infant's medical team, the research team might need to do Step 2 before Step 1, as described above. There will be at least 24 hours period between the two steps.

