- DSMB report will be submitted to NIH within one week after each quarterly scheduled meeting. However, any action by the DSMB resulting in a temporary or permanent suspension of the clinical study will be reported to the NIH Program Official responsible for the grant within 48 hours. Any death will requires expedited reporting to NIH program officer within 24 hours of study's knowledge of death.

Reportable Adverse Events, including Serious Events

Definitions

Adverse Event (AE), also referred to as an adverse experience, is any untoward medical occurrence in humans, whether or not considered intervention related, which occurs during the conduct of a clinical trial. Any change in clinical status, routine labs, x-rays, physical examinations, etc., that is considered clinically significant by the study investigator is considered an AE. Adverse events will include: hypothermia (defined as temp less than 35.5 degree C), abnormal changes in vital signs including respiratory rate (apnic episodes or respiratory rate more than 70/min), heart rate (less than 70/min or more than 220/min), and oxygen saturation (less than 85%), . The staff nurses normally records any abnormal vital signs findings as part of their routine NICU care for all babies. These data will continuously be recorded during the cold feeding (usually around 15 minutes). Changes in vital signs can be a routine and frequent occurrences in preterm babies as part of their pathophysiology, The following AEs if occurred during the cold feeding will result in study termination for that baby and notification of the DSMB committee:

- 1- Any incidence of hypothermia
- 2- More than 2 episodes of apnea
- 3- Tachypnea defined as increase respiratory rate more than 70/min for more than 2 minutes
- 4- More than 2 episodes of bradycardia (defined as HR less than 70 for more than 10 seconds).
- 5- Tachycardia (defined as HR more than 220) for more than one minute

6- More than 2 episodes of desaturation (defined as O2 saturation less than 85%) for more than 30 seconds

Serious Adverse Events (SAEs), as determined by the PI, are any event that results in any of the following outcomes:

- 1. Death
- 2. Life-threatening SAE (life-threatening means that the study participant was, in the opinion of the investigator, at immediate risk of death from the reaction as it occurred)
- 3. Inpatient hospitalization or prolongation of existing hospitalization

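### The automatic hypothermia stop applies only during the cold feed, so the Step 1 temperature readings at 10 and 30 minutes afterwards cannot trigger it

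*Combined protocol and SAP*

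**What the plan says.** The definition of hypothermia as an adverse event carries no time limit: "Adverse events will include: hypothermia (defined as temp less than 35.5 degree C". The rule that removes an individual infant does. Its lead-in reads "The following AEs if occurred during the cold feeding will result in study termination for that baby and notification of the DSMB committee", and six items follow. Hypothermia is the first, and a single occurrence is enough. The same paragraph puts the usual length of the cold feeding at around 15 minutes.

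The Step 1 temperature schedule is in Section 4, Study Design: "The axillary temperature will be measured immediately prior to and after each feeding condition". For the cold feed it adds: "It will also be measured at 10, and 30 minutes after the CS feed".

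Step 2 normally follows 24 to 48 hours later. It gives cold barium, then up to 15 minutes of chilled milk if the swallow improves, then more cold barium, with axillary temperature taken every 10 minutes. Section 4 also allows Step 2 to come first: "There will be at least 24 hours period between the two steps".

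**The concern.** Section 2 (Cold Stress Prevention) presents the repeated temperature checks as the protection against cold stress, so a low reading at one of those checks would be expected to have a stated consequence for that infant. As written, a temperature below 35.5°C ends participation if found during the feed. The same temperature first found 10 or 30 minutes later has no automatic consequence.

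A window limited to the feed suits heart rate, breathing and saturation, which can be watched continuously. It does not suit a temperature taken at fixed times around the feed. At stake is a second cold exposure, about a day or two later, for an infant who has already cooled after the first.

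**Working it through.** No figure in the plan is in dispute. The check sets the window of the rule against the schedule of readings, then looks for any other rule that would close the gap.

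**Step 1 readings around the cold feed (Section 4)**

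| Axillary reading | Taken during the feed? | Can it trigger the automatic stop? |
|---|---|---|
| Immediately before | No | No |
| Immediately after | Not literally | Arguable |
| 10 minutes after | No | No |
| 30 minutes after | No | No |

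Count: 1 + 1 + 2 = 4 readings, with 0 scheduled during the feed. Two are clearly past the window. On a literal reading, 1 + 2 = 3 are.

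**Step 2 readings.** The rule is not confined to Step 1. With checks every 10 minutes and a feed of up to 15 minutes, one or two readings fall inside a full-length feed (15 / 10 = 1.5). Hypothermia found then does end participation. Any check after the feed ends is outside the window, as in Step 1.

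**Other rules that might bar the remaining step**

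- Exclusion criteria (Section 5): nothing on temperature or on a reaction to an earlier cold feed.
- Step 2 entry (Section 4): depends on the routine swallow study. "If no dysfunction is noted, the procedure will end, and the child will no longer be eligible for further participation in this research study".
- Step 2 continuation (Section 4): if the dysphagia does not improve on the first cold swallows, "the study would end, and the child will no longer be eligible for participation further in this research study". This is also a swallowing criterion.
- Stability clearance by the attending neonatologist (Section 5; Principal Investigator Responsibilities): a check on the individual infant, but with no temperature threshold and no reference to Step 1 results.
- Adverse event review (Assessment of Severity): the PI judges seriousness, severity and causality, and the DSMB acts as it sees fit. No deadline is set for the DSMB to act on a non-serious event, and its emergency meetings are tied to serious ones.
- Study Halting/Termination: needs a serious adverse event, adverse events judged excessive, or a DSMB decision to halt. It stops the study; it is not a rule for one infant.

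None of these makes a low reading after the feed an automatic bar to the remaining cold exposure. Each either turns on something else or leaves the decision to judgment.

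**The case against.** The strongest reply is that the protocol already responds to such a reading and that leaving re-exposure to clinicians is a defensible choice. Much of this stands. The event is a named adverse event whenever it occurs, the IRB is told immediately, and events are to be reported within 24 hours. With at least 24 hours between steps, a Step 1 event should normally be known before Step 2. Re-exposure is also guarded: "A neonatologist will be next to the baby at all times", temperature is checked every 10 minutes, and the automatic stop applies again during that feed. These safeguards keep the point minor. They do not replace a rule: the 24-hour limit governs reporting, not a DSMB decision, and Step 2 monitoring would detect a second episode rather than prevent the exposure.

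A second reply is that the drafters meant the whole feeding episode, including its follow-up checks; otherwise the hypothermia item does little in Step 1. That may be the intention, but the lead-in does not say so. The statement that data are recorded continuously during the cold feeding follows a list that includes hypothermia, so it might be read as covering temperature. Even then, the 10 and 30 minute readings remain outside the window.

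A reader might infer that a late low temperature is simply ignored, or that Step 2 has no temperature exit at all. The documents support neither: the adverse event process covers the first, and the stopping rule covers the Step 2 cold feed.

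**Conclusion.** The point holds as a mismatch between a stopping rule and the readings meant to inform it. Two of the four Step 1 cold-feed readings, or three if the lead-in is read literally, cannot trigger the automatic stop. No other written rule then keeps the infant from the remaining step. It matters in practice when Step 1 comes first and the routine swallow study is positive, or when Step 2 comes first and the low reading falls after its feed.

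Severity is minor. The documents give no frequency for delayed hypothermia, and Sections 2 and 5 report no cold-stress signal in earlier studies, so no probability can be attached. A reader might see a major safety failure here; the clinical safeguards do not support that. The point does not bear on the primary endpoint, its analysis or the sample size calculation. It rests on reading the lead-in as governing all six listed events, which is its plain sense.

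**What to change.** Under Reportable Adverse Events (Definitions), amend the hypothermia item only. Keep the existing consequence, which is ending that infant's participation and notifying the DSMB. Apply it to any axillary reading below 35.5°C from the start of a cold exposure through the last scheduled post-feed reading: 30 minutes after the feed in Step 1, and the last 10-minute check of the session in Step 2. State that it applies whichever step comes first. Leave the five vital-sign triggers unchanged.

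The cost is one sentence, with no new measurements and no additional infants. An occasional infant may be withdrawn before the remaining step. If Step 1 came first and that infant would have had a positive swallow study, the primary comparison loses one infant. If the randomised order put the cold feed first within Step 1, that infant's room-temperature feed is lost too. How often this would happen cannot be stated from the documents.
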